3.2 Identification and description of the investigational medical device

In this study, the following medical device will be tested:

Steriwave™ Nasal Photodisinfection System
Ondine Biomedical Inc., Vancouver, Canada.

It consists of three parts with the corresponding model numbers (shown in **Figure 1**):

SW4000 Light Source
SW3200 Nasal Light Illuminator (single-use)
SW3100 Formulation Applicator (single-use)
photosensitizer: methylene blue

Figure 1 (Steriwave™ instructions for use, page 5; Ondine Biomedical Inc.)

COMPONENT FUNCTIONS

LIGHT SOURCE

The Light Source generates the red light used to activate the disinfecting formulation. The Light Source controls function as follows:

Buttons

[figure not shown]
[figure not shown]
Buttons	Function	Action
	Standby	Press to initialize the Light Source. Press to reset the Light Source.
	Start	The Start button will flash when the Light Source is in READY mode. Press the Start button to begin illumination.
	Stop	During illumination, the Stop button may be pressed at any time to stop light emission.

LED Display

Indicator	Indication	Action required
	Connector Symbol Flashing	Connect the NLI to the Light Source. The indicator will disappear when the NLI is properly connected.
	Blue Snowflake Illuminated	Light Source is too cold. Allow the Light Source to come to room temperature.
	Yellow Attention Illuminated	Error – Light Source operation is outside nominal ranges. Press Standby to reset the Light Source. If error persists, contact manufacturer for assistance.

[figure not shown]
Connector Block & Umbilical Cable – Type B Applied Part, connects the Light Source to the NLI.

Mains Power Cord (hospital grade) – connects the Light Source to electrical power.

[figure not shown]
NASAL LIGHT ILLUMINATOR (SINGLE-USE)

Type B Applied Part
NLI delivers the red light illumination to the patient's nose.
Light diffuser tips – provide comfort end-points to the cable.
Fiber optic cable – delivers the red light illumination.
Connector – provides the cable connection to the Light Source.

FORMULATION APPLICATOR (SINGLE-USE)

Single-use tube containing formulation applicator swab – provides disinfection photosensitizer formulation.

PATIENT EYE PROTECTION

Eyewear – Protects patient's eyes from formulation splatters or accidental eye contact of NLI.

INSTRUCTIONS FOR USE

SW9000-001 Rev E | 5

The medical device bears a conformity marking (CE label) and is thus approved for medical use. Its intended use is aPDT of the nose and nasopharynx after topical application of a photosensitizer (methylene blue). No deviations from the original CE-marked instructions for use will be made in this study. No changes will be made to the design of the device.

The nasal light illuminator and the formulation applicator preloaded with the photosensitizer, which both are single-use disposable products, are the two parts of the device that get in contact with human tissue and body fluid (nasal secretion).

The manufacturer has provided training on the use of the medical device. All investigators and study personnel involved in the use of the medical device have been sufficiently trained and are experienced in the use of the device. All investigators and all members of the clinical study personnel have been provided with a copy of the instructions for use.

3.3 Preclinical evidence

Since the medical device carries a conformity marking (CE label) and there is no off-label use, preclinical evidence can be omitted in the CIP. Data from the manufacturer (Ondine Biomedical Inc.) can be obtained upon request.

3.4 Clinical evidence to date

Adverse device effects

No serious adverse events were reported in >150,000 treatments in Canada, where the medical device is considered standard by Health Canada. Minor adverse events included a runny nose, sneezing, irritation, etcetera, and were self-limited.

Toxicology: A review of literature toxicity data for methylene blue suggests that the toxicity of the compound, if any, comes from doses or concentrations of 5,000 µg/mL or more along with light irradiation of >500 J/cm². By comparison, the nasal photodisinfection treatment will be applied at a maximum concentration of 100 µg/mL and approximately 160 joules total of light energy or 360J/cm². This minuscule dose of maximum 100 µg/mL is also safe during pregnancy with no reported adverse event in pregnant woman for oral or nasal methylene blue formulation over the past 15 years of use.

Light disturbance: The light emitted by the medical device is not harmful to the eyes.

History of modification or recall

The photosensitizer formulation, swabs, and the patient-contacting nasal illuminator device remained unchanged throughout the entire marketing history in Canada. While the laser light source has evolved over three models, the laser diode wavelength, light dosimetry, and light path have remained unchanged throughout.

Post-marketing data

Post-marketing studies focused on various infectious agents residing in the nose, particularly multi-drug resistant bacteria. Studies found high efficacy against multidrug-resistant *Staphylococcus aureus* (MRSA) (Bryce et al, 2014; Street C, 2009 and 2010).

3.5 Justification for the design of the clinical investigation

Today there is no standardized protocol for nasal cavity decolonization. With our study design analyzing the microbial decontamination and test the applicability in the preoperative setting under general anesthesia allows gaining valuable information to establish a standardized disinfection protocol for the nasal cavity.

Combining the study intervention with a surgical intervention in the head and neck area allows for minimal stress on the patient. After the second swab test the study intervention is followed by regular disinfection protocol as performed according to today's hygiene standards at University Hospital Zürich.

aPDT must be performed within established limits for light power, light time, and photosensitizer concentration and dosage. All settings in this study are based on the manufacturer's instructions for use and correspond to the standard of care in Canada, where the medical device is routinely used, as well as to the CE-labeled instructions of use.

Light power: The power is set at 150 mW/cm². This value has been shown to have an antimicrobial effect in various nostril sizes without thermal effects on the nasal tissues. The wavelength of the device is set at 663 nm which is the optimal excitation wavelength for activation of methylene blue.

Light time: A double two-minute treatment cycle (total 4min illumination) is selected to ensure appropriate therapeutic effect regardless of nasal cavity size, biofilm thickness, anatomical variances, or increased mucus layers.

Photosensitizer concentration: 0.01% methylene blue is used for this study, which corresponds to 100µg/ml. This concentration reflects a balance between sufficient photosensitizing effect and increasing light blockade. Methylene blue shows peak light absorption at 660 nm wavelength (red light). As a cationic molecule, it is attracted to negatively charged surface structures and preferentially binds to them. This keeps the aPDT reaction tightly confined to the targets, as microbial surfaces are usually negatively charged, compared to human tissue cells. When exposed to red light, the methylene blue can transfer light energy to surrounding molecular oxygen in the tissue, which in turn generates short-lived reactive oxygen species. They are lethal to microbial cell membranes while they have only little effect on eukaryotes (Cieplik, 2018).

Photosensitizer dosage: One formulation applicator (soft swab pre-saturated with photosensitizer) will be applied to each nostril (one right, one left) prior to the first two-minute light treatment. This sequence is repeated with repositioned light delivery tips to achieve maximum coverage of the nose. The maximum dose of the photosensitizer formulation per treatment is calculated as follows:

- 2 saturated swabs of 1.5 ml each = 3.0 ml of formulation
repeated once = 6.0 ml of formulation
- 0.01% methylene blue solution = 600µg total dose, assuming complete absorption
for a 70 kg adult, this represents 0.014 mg/kg/day

- an average patient treated for methemoglobinemia would receive about 1-2 mg/kg methylene blue; the topical nasal decolonization dosage is hence less than 1/200th of the i.v. dose for methemoglobinemia treatment.

3.6 Explanation for choice of comparator

In our study, there will be a comparison of every patient pre- and post-intervention (nasal swab test for microbial analysis). Therefore, the individual microbial decontamination will be analyzed. To reduce bias of concomitant treatment / medication and the disinfection effect of chlorhexidine gluconate, patient randomization either to experimental or control group is mandatory.

3.7 Risk evaluation (benefit-to-risk rationale)

Anticipated adverse device effects

The photosensitizer used for aPDT in this study (methylene blue with chlorhexidine gluconate) has been approved as a complete System by the appropriate agencies and both ingredients have been shown to be effective against microbial colonization. The photosensitizer formulation has been used on patients for many years with a minimum of reported adverse events. It is used by Orcos-Dental in Switzerland, and it is even approved for i.v.-use. Chlorhexidine is listed in Annex V in the List of preservatives as approved. The concentration of the active ingredient (0.01% methylene blue) is many times lower than when the same products are used separately, for example for classical surgical site disinfection (chlorhexidine) or treatment of methemoglobinemia (methylene blue). The used system is certified in the European Union and in Canada.

In Canada in thousands of patients, there is considerable real-world data on the adverse event profile. Data from 49'313 nasal aPDT treatments in an industrial setting (meat industry) showed that 49'009 treatments were not associated with any adverse events. 304 (0.6%) minor adverse events were reported during treatment and 2'214 (4.5%) in the 24 hours after treatment as shown in **Table 2**. No serious adverse events occurred.

Reported minor adverse events included a runny nose (1.9%), sneezing (1.3%), nasal irritation (0.5%), and throat irritation (0.3%) and were all self-limited. Less commonly reported adverse events included local itchiness, nasal congestion, altered smell and/or taste, feeling of warmth, cough, headache, or nosebleed.

Table 2: Reported adverse events from a nasal aPDT study in Canada (Ondine Biomedical Inc.)

	During Treatment		Within 24 Hrs		Total	
Total # of Survey responses	49,313	100.0%	48,841	100.0%		
No Side Effects	49,009	99.4%	46,627	95.5%		
Had Side Effects	304	0.6%	2,214	4.5%		
Total # of Side Effects	313	0.6%	2,702	5.8%	3,015	6.1%
Expected	246	0.5%	2,087	4.5%	2,333	4.7%
Runny nose	32	0.1%	909	1.9%	941	1.9%
Sneeze	57	0.1%	603	1.3%	660	1.3%
Nose irritation	71	0.1%	188	0.4%	259	0.5%
Throat irritation	24	0.0%	130	0.3%	154	0.3%
Itchy nose	35	0.1%	110	0.2%	145	0.3%
Nasal congestion	1	0.0%	96	0.2%	97	0.2%
Itchy throat	11	0.0%	31	0.1%	42	0.1%
Odd smell/taste	2	0.0%	12	0.0%	14	0.0%
Warm feeling	8	0.0%	2	0.0%	10	0.0%
Watery eyes	3	0.0%	3	0.0%	6	0.0%
Cough	1	0.0%	1	0.0%	2	0.0%
Noticeable blue stain around nostrils	1	0.0%	1	0.0%	2	0.0%
Clear nasal passage			1	0.0%	1	0.0%
Unexpected	67	0.1%	615	1.3%	682	1.4%
Headache	3	0.0%	270	0.6%	273	0.6%
Dry nose	24	0.0%	152	0.3%	176	0.4%
Dry throat	11	0.0%	83	0.2%	94	0.2%
Nose bleed	23	0.0%	48	0.1%	71	0.1%
Dizzy	2	0.0%	21	0.0%	23	0.0%
Red / blood-tinged mucus	2	0.0%	14	0.0%	16	0.0%
Drowsy	1	0.0%	4	0.0%	5	0.0%
Furunculosis (pimple in nose)			4	0.0%	4	0.0%
Itchy			3	0.0%	3	0.0%
Uncomfortable	1	0.0%	2	0.0%	3	0.0%
Increased acne			2	0.0%	2	0.0%
Sense of smell is diminishing			3	0.0%	3	0.0%
Vomit			1	0.0%	1	0.0%
Fever/flu			1	0.0%	1	0.0%
Swelling in the eye			1	0.0%	1	0.0%
Heart rate increase			1	0.0%	1	0.0%
Anxiety			1	0.0%	1	0.0%
Hard to breathe / Shortness of breath			2	0.0%	2	0.0%
Stomach ache			1	0.0%	1	0.0%
Triggered sinusitis			1	0.0%	1	0.0%
Other - unspecified	25	0.1%	46	0.1%	71	0.1%

Results of phase 2 nasal photodisinfection trial. Full title: Bacterial Eradication of the Nasal Epithelium From Infectious Toxins With PDT (BENEFIT-PDT); Ondine Biomedical Inc., Vancouver, Canada (<https://clinicaltrials.gov/ct2/show/NCT05090657>)

Risks due to interaction with concomitant treatments

Methylene blue is administered intravenously for the treatment of methemoglobinemia. From this use, data is known on interactions with pharmacologic agents that act on serotonin metabolism. These include selective serotonin reuptake inhibitors (SSRIs) and other types of antidepressants. The risk of serotonin syndrome exists in patients taking serotonergic drugs when methylene blue is used at doses exceeding 5 mg/kg. In this study the estimated dosage of methylene blue is under 0.1 micrograms per kg, and it is being administered topically in the nasal cavity. Regarding the applied topical dose an exclusion of patients with SSRI medication is not necessary.

Risks due to microbiological testing

Swabbing of the anterior nose can in rare cases lead to a nosebleed due to superficial injury of the sensitive nasal mucosa.

Measures to control or mitigate the risks

Patients with known allergies to any of the photosensitizer's ingredients (methylene blue, chlorhexidine) are excluded from this study.

History of modification or recall in relation to safety and clinical performance

The photosensitizer formulation, swabs, and the patient-contacting nasal illuminator device remained unchanged throughout the entire marketing history in Canada. While the laser light source has evolved over three models, the laser diode wavelength, light dosimetry, and light path have remained unchanged throughout.

Anticipated clinical benefit

Nasal decolonization is known to reduce the risk of healthcare-associated infections and is routine care in many Canadian hospitals. A standardized protocol to disinfect the nasal cavity could reduce surgical site infections. In addition, it could be useful in eliminating multi resistant pathogens in the nasal cavity such as MRSA.

Benefit-risk rationale

Both individual patients (reduced likelihood of surgical site infection; unknown colonization with multi resistant pathogens) and future subjects (standardized protocol for preoperative nasal cavity disinfection) may benefit from participation in this study.

Risks to patients are minor treatment-related adverse effects that are self-limiting. The addition of nasal cavity aPDT in the preoperative disinfection protocol has a good benefit-risk ratio. The choice of light intensity and light duration as well as the testing of light power output before every treatment ensure sufficient efficacy of the medical device.

3.8 Justification of the choice of the investigation population

Microbial colonization of the nasal cavity poses a risk for surgical site infection during interventions in the oral cavity. Therefore, additional disinfection of nasal cavity and upper respiratory tract could be beneficial.

Inclusion of all patients undergoing surgery in general anesthesia in the Oral and Maxillofacial Surgery Department who meet the inclusion/exclusion criteria without further selection for age, gender, or co-morbidities will ensure adequate community representation in this study.

No vulnerable subjects (minors, subjects incapable of judgment or subjects under tutelage) will be included in this study. Patients will be informed about this study during regular consultation prior to surgery. Consent to the study can be withdrawn at any time.

Pregnant and breastfeeding women will be excluded from the study. Pregnancy induces significant physiological alterations, such as increased blood volume and nasal tissue engorgement (hyperemia) which could influence the clearance of the nasal mucosa and therefore influence the study results. Regarding the risks of topical application of methylene blue during pregnancy the minuscule dose of maximum 100 µg/mL is substantially lower than doses administered intravenously for conditions like methemoglobinemia (1-2 mg/kg). Based on the concentration applied topically and no reported adverse event in pregnant woman for oral or nasal methylene blue formulation over the past 15 years of use, it can be stated safe during pregnancy. We therefore believe that a pregnancy test before inclusion in the study is unjustified for all women of childbearing age. If pregnancy is reported in the survey, the patient will be excluded.

4. CLINICAL INVESTIGATION OBJECTIVES

4.1 Overall objective

Currently, the standard preoperative disinfection protocols for the nasal cavity varies from no disinfection at all to inconsistent application methods and disinfection solutions such as chlorhexidine, povidone-iodine, Octenidindihydrochlorid or alcohol-based antiseptics. In the department for Oral and Maxillofacial Surgery and the department for Otho-Rhino-Laryngology the standard of care is no disinfection for the nasal cavity even if open surgery within the nose is carried out. To standardize a relatively user-independent protocol aPDT with its advantageous lack of resistance formation will be tested for applicability.

4.2 Primary objective

The primary objective is to determine the additional efficacy of nasal cavity photodisinfection in reducing local microbial nasal colonization in a preoperative setting compared to 0.2% chlorhexidine gluconate and non-light activated methylene blue. Comparison of the 5 minutes after aPDT measure to the control group and to the baseline 3 minutes prior to intervention.

4.3 Secondary objectives

The secondary objectives are to:

- To determine the efficacy of nasal cavity photodisinfection as an add-on treatment to 0.2% chlorhexidine gluconate in reducing local microbial colonization after 14 (+/-1) days follow-up.
- To analyze short term effects in the critical time for wound healing after 2 days in the subgroup after fracture reduction of the midface
- Longitudinal comparison of microbial colonization at baseline, 5 minutes after aPDT and 14 (+/-1) days after aPDT.
- develop an aPDT disinfection protocol for preoperative nasal cavity disinfection at University Hospital Zürich

4.4 Safety objectives

The safety of nasal aPDT will be measured. Patients will be monitored for any untoward effects related to the nasal decolonization using aPDT.

5. CLINICAL INVESTIGATION OUTCOMES

5.1 Primary outcome

To objectively determine the efficacy of nasal cavity decolonization with aPDT in eliminating or significantly decreasing pathogens, relative abundance of CFU (colony forming unit) over nine analyzed microbe groups at timepoint 5 minutes after intervention, are grouped as score ranging from 0-27. The results will be adjusted to the baseline measure 3 minutes pre-intervention. Comparing bacterial colonization scores of interventions to control group allows to measure additional disinfection effect of aPDT over chlorhexidine gluconate.

Score bacterial colonization:

Name	CFU's	Score
"not detectable"	below detection limit	0
"sporadic"	<10 ⁴	1
"moderate"	10 ⁴ – 10 ⁵	2
"plentiful"	>10 ⁵	3

Nine microbial subgroups for analysis:

1. β -hemolytic (group A and group B) *Streptococcus*
2. *Staphylococcus aureus* (with discrimination in MSSA and MRSA)
3. Coagulase negative *Staphylococcus* species (incl. *Staphylococcus epidermidis*)
4. α -hemolytic *Streptococcus* species (oral or viridans-group *Streptococci*)
5. *Corynebacterium* species
6. *Candida* species
7. *Enterobacteriales*
8. *Actinomyces* species and miscellaneous aerotolerant bacteria
9. Anaerobic bacteria with focus on *Propionibacterium*

5.2 Secondary outcomes

Bacterial colonization 14 (+/-1) days after aPDT across the nine analyzed microbe groups and expressed as score (range 0-27).

Bacterial colonization 2 days after aPDT in the midface trauma subgroup across the nine analyzed microbe groups and expressed as score (range 0-27).

5.3 Safety outcomes

Standardized survey for adverse effects noted after treatment and on day 1 and day 14 (+/-1) during regular follow-up consultation after surgery. For outpatient procedures, side effects are surveyed after treatment on the first day as a telephone conversation.

6. CLINICAL INVESTIGATION DESIGN

6.1 General clinical investigation design and justification of design

Design and rationale

This is a randomized controlled prospective study. Randomization of participants to either experimental or control group is necessary to reduce bias caused by concomitant treatment / medication and to investigate the additional effect of aPDT (activated photosensitizer) over the disinfection effect of chlorhexidine gluconate or unactuated methylene blue.

Intended procedures

Preoperative consultation:

After patient information and obtaining of informed consent, the inclusion and exclusion criteria are checked, and patient demographic data and medical history are obtained. Data will be taken from their medical records in the clinical information system (KIS).

Surgery day:

Random assignment of patients to experimental or control group.

Consent to participate will be updated after admission to the hospital on the day of surgery.

After Intubation and during positioning and final preparations for surgery, participants will then be administered the medical device as described under 8.1.1 Experimental Intervention (medical device) depending on assignment to experimental or control group (no light activation in control group).

Participants will be asked about their subjective evaluation of the treatment on the first postoperative day (Visit 2). For outpatient procedures, the survey is carried out by telephone.

Additional nasal swab for the subgroup after open reduction and internal fixation of midfacial fracture on day 2 (Visit 3; day of hospital discharge)

Visit day 14 (+/- 1)

Participants will be revisited 14 days (+/-1 d) after intervention (Visit 4) as part of the regular follow up consultation. The appointment will be made before discharge from the hospital. All participants will be interviewed about possible adverse effects and a third nasal swab test for microbiological analysis will be performed.

Limitations of the design

The main limitation of this design is the risk of misattributing immediate adverse effects when study intervention is combined with surgical intervention under general anesthesia. Therefore, initial survey is carried out on the first postoperative day ("Visit 2") to reduce misinterpretation of surgery related symptoms. Exclusion of nasal intubation or surgery in the nose further reduce surgery or anesthesiology related effects. With an additional more homogenous subgroup of patients after open reduction and internal fixation of midface fractures, we can reduce these influences and gain additional information in the early phase after aPDT on day 2 (day of hospital discharge). On the other hand, combining intervention and study keeps the number of lost patients to follow-up limited and therefore allows also conclusive analysis of later adverse events (till 14 days post intervention).

Population

Patients undergoing surgery in general anesthesia at Maxillofacial Surgery Department of University Hospital Zurich will be included in this study. There will be 208 patients enrolled in this study (experimental group n=104, control group n=104). The target sample size is expected to reflect the demographic characteristics of the local community in terms of age, gender, and comorbidities.

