7.4 Criteria for withdrawal / discontinuation of subjects

Withdrawal of subjects

If a clinically significant finding is identified after enrollment in the study (including, but not limited to changes from baseline), the principal investigator or qualified designee will determine if any change in participant management is necessary. Any new clinically significant finding will be reported as an adverse event (AE).

Participants are free to withdraw from participation in the study at any time upon request.

An investigator may exclude or withdraw a participant from the study for the following reasons:

- significant non-compliance with the study intervention due to intolerance of the nasal illumination
- if any clinical adverse event or other medical condition occurs such that continued participation in the study would not be in the best interest of the patient

The reason for the participant's discontinuation or withdrawal from the study will be recorded in the Case Report Form (CRF). Subjects who sign the informed consent form and are enrolled in the study, but do not receive the study intervention, may be replaced. Subjects who receive the study intervention and subsequently withdraw, or are withdrawn or discontinued from the study, will not be replaced.

Patients lost to follow-up

Participants are considered "lost to follow-up" if they fail to report for scheduled study visits and cannot be reached to complete all protocol-required study procedures.

The following actions will be taken if a participant fails to attend a required study visit:

- The investigator will attempt to contact the participant and reschedule the missed visit for 1 day. These contact attempts will be documented in the participant's study file.
- Should the participant continue to be unreachable, they will be considered to have withdrawn from the study with a primary reason of "lost to follow-up".

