8.1.1 Experimental intervention (medical device)

The intervention consists of the following steps:

1. Swabbing the formulation applicator (soft swab pre-saturated with the photosensitizer formulation) into patient's nostrils.
2. Connection of the nasal light illuminator to the light source and insertion of the nasal light illuminator into the patient's right and left nostrils.
3. Activation of the light source and illumination of the nose and nasopharynx for 2 minutes.
4. Repetition of steps 1.-3. to complete photodisinfection of all nasal regions.

Duration of treatment: 14 minutes

- pre-intervention nasal swab test (0.5 min)
- waiting time (3 min)
- nasal application of photosensitizer (0.5 min)
- 2min illumination
- Repetition of photosensitizer application (0.5 min)
- 2 min illumination
- Waiting time (5 min)
- Post-intervention nasal swab test (0.5 min)

All treatment steps follow the CE-labeled instructions for use of the medical device. There are no deviations from the commercial product. The corresponding part of the instructions for use provided by the manufacturer is shown in **Figure 2**.

The procedure will be performed by the investigators (physicians or clinical study nurses with special training provided by the manufacturer of the medical device).

All investigators and clinical study nurses have been trained by the manufacturer in the use of the medical device and its components. All consumables will be disposed of in accordance with hospital hygiene standards and treated as contaminated with infectious materials. The light source will be wiped down with the standard disinfectant solution provided by the hospital. Before starting the intervention, the optical power output will be checked with the manufacturer's approved power tester to ensure that the optical output power meets the technical specifications.

Figure 2: Steriwave™ instructions for use (pages 6 and 7; Ondine Biomedical Inc.)

PROCEDURE

Use the following instructions to perform the nasal photodisinfection procedure.

SETUP

- 1 Position the Light Source to ensure the light diffuser tips of the fiber optic cable can reach the patient's nose without tension. Ensure Light Source air vents are not obstructed.
- 2 Connect the Light Source power cord to mains power outlet. Ensure cord is not a tripping hazard.

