9.3 Procedures at each visit

9.3.1 Screening visit (Visit 0)

The screening visit takes place as part of the regular consultation hours for Oral- and Maxillofacial Surgery. Patients will be informed about the study. Informed consent will be obtained. Inclusion and exclusion criteria will be reviewed. Demographic information, patient's medical history and survey of concomitant treatments will be obtained.

9.3.2 Visit 1

The first visit will take place during preparation for surgical intervention. Patient is already under general anesthesia. Randomization takes place according to description 6.2.1.

Nasal swab + aPDT

Nasal swab test 3 minutes before the study intervention as described under 8.1.3. Administer study or control intervention as described under 8.1.1 and 8.1.2.

Nasal swab + follow up

After treatment, a second nasal swab test (5 minutes post intervention) for analysis of primary outcome will be taken.

In case of AE / SAE and/or device deficiencies the corresponding eCRF forms are recorded.

9.3.3 Visit 2

The second visit will take place on first postoperative day. The study investigator (not the same investigator who carried out the study intervention) will record the survey of concomitant treatment, survey of expected side effects and AE / SAE. In addition, scheduling of visit 3 on day 14 (+/- 1) post intervention is carried out. For outpatient procedures, visit 2 is carried out by telephone.

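### Allocation is listed before the baseline swab, and sections 6.1 and 9.3.2 disagree on when on the surgery day it happens, so the baseline can be sampled with the arm known

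*Combined protocol and SAP*

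**What the plan says.** **Section 6.1.** Consent comes at the preoperative consultation: "After patient information and obtaining of informed consent, the inclusion and exclusion criteria are checked". Under the surgery day, the first item is "Random assignment of patients to experimental or control group". The second is "Consent to participate will be updated after admission to the hospital on the day of surgery". Intubation and the device procedure follow.

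**Section 9.3.2 (Visit 1).** "Patient is already under general anesthesia. Randomization takes place according to description 6.2.1". The next item is "Nasal swab test 3 minutes before the study intervention as described under 8.1.3".

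**Table 1.** Randomisation and the first nasal swab share the Visit 1 column, at minus 3 minutes. No order is given within the column.

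**Blinding (6.2.1, 6.2.2).** The patient is blinded by anaesthesia. The clinicians who run the postoperative surveys cannot see the randomisation form and are not the people who treat. Nothing is said about concealing the arm from whoever takes the swabs in theatre.

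**Where the arms part (8.1.1, 8.1.2).** Applicator, formulation and illuminator insertion are the same. The arms differ only in whether the light is switched on.

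**Losses before treatment (7.4, 11.4.1).** Subjects who consent and are enrolled "but do not receive the study intervention, may be replaced". The full analysis set (FAS) is limited to randomised patients who went through aPDT.

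**The concern.** A baseline is safe to adjust for because randomisation makes it independent of the arm. That holds if it is measured before allocation, or by someone who does not know the allocation. Here neither is assured. How much material a swab picks up depends on how it is done, and routine laboratory processing cannot undo a difference in sampling. A more thorough baseline swab in the aPDT arm would raise that arm's baseline and flatter the adjusted effect; a lighter one would do the reverse. The documents give no reason to expect either direction. Section 6.2 nevertheless states that bias in determining colonisation status is not reasonably likely.

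The second strand is timing. If allocation really preceded the consent update and intubation, as the list in 6.1 reads, a refusal or a late eligibility failure would fall after allocation. Such a patient would leave the FAS and could be replaced. Decisions by staff who know the arm could then shape who is analysed.

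**Working it through.** **1. Is there room to allocate after the baseline swab?** The timed steps in 8.1.1 are baseline swab 0.5, wait 3, application 0.5, light 2, application 0.5, light 2, wait 5, final swab 0.5.

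0.5 + 3 + 0.5 + 2 + 0.5 + 2 + 5 + 0.5 = 14 minutes, which is the stated duration.

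The baseline swab ends at 0.5 minutes. The arms first differ when the light is or is not switched on, at 0.5 + 3 + 0.5 = 4 minutes. The arm is therefore not needed for 4 − 0.5 = 3.5 minutes after the baseline swab, of which 3 minutes are an idle wait. The control schedule in 8.1.2 has the same timings. Earlier allocation serves no step of the procedure.

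**2. What order do the documents give?**

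| Place | Randomisation relative to consent update | Relative to intubation | Relative to baseline swab |
|---|---|---|---|
| 6.1 | listed before | listed before | swab not listed separately |
| 9.3.2 | after, by implication (patient anaesthetised) | patient already under anaesthesia | listed before |
| Table 1 | no order | no order | same column |

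A patient under general anaesthesia cannot update consent, so 6.1 read as a sequence and 9.3.2 cannot both be right. No visible text puts allocation after the baseline swab.

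**3. Which analyses use the baseline score?**

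- Exact Wilcoxon-Mann-Whitney test and the Mann-Whitney parameter (11.4.2): not used.
- Additional proportional odds model (11.4.2): adjustment for baseline is its stated purpose, and 5.1 also says results are adjusted for it. A later sentence in 11.4.2 names only surgery type and treatment as explanatory variables; I take the stated purpose as governing.
- Subgroup split at the median baseline (11.4.3): used.
- Comparison with the pre-intervention measure (4.2) and the longitudinal comparison (4.3, 9.2.2): used.

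**4. Is power the issue?** The enrolment figure reproduces. The t-test needs 85 per arm, or 170. Then 170 / 0.864 = 196.8, raised to the even number 198, and 198 × 1.05 = 207.9, or 208 (198 / 0.95 = 208.4 is within one patient).

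For loss fraction L, the effective size per arm is n = 104 × 0.864 × (1 − L), and power ≈ Φ(3 / (6√(2/n)) − 1.96). The documents give no L for the interval between allocation and treatment, so these values are assumptions to show the range:

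| Assumed L | Power |
|---|---|
| 0% | 91.8% |
| 5% | 90.4% |
| 10% | 88.9% |
| 20% | 85.0% |

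The 5% allowance absorbs modest loss. What matters is who is lost and who decides, not the count.

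**The case against.** The strongest reply is that 9.3.2 is the operative description of Visit 1 and settles the matter. Allocation happens under anaesthesia, so the consent update is already done, and intubation would ordinarily be done too. Only a short interval in theatre remains, for example a failed insertion. **This stands.** A reader might infer from 6.1 that patients are randomised before agreeing to take part. The documents do not support that: initial consent precedes everything, and the order of allocation and consent update in 6.1 rests on list position alone.

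Second, even on the 6.1 order nothing says patients learn their arm, so a refusal need not depend on it. **This also stands.** The route to bias is a decision by staff who know the arm, not the patient's refusal.

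Third, the main test ignores the baseline. **True**, and it limits the reach of the point.

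Fourth, the flow chart in section 9.1 is not visible in the text available here and may show an order within Visit 1. **That is possible.** It would not remove the disagreement between 6.1 and 9.3.2.

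What the reply leaves untouched is the baseline swab. Section 9.3.2 itself lists it after randomisation, and no text conceals the arm from the person taking it.

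**Conclusion.** The point holds as a low-cost correction to sequence. As written, the baseline score can be sampled with the arm known. This exposes the adjusted proportional odds model, the baseline subgroup and the pre/post comparisons, but not the Wilcoxon-Mann-Whitney test. Separately, 6.1 and 9.3.2 conflict and must be reconciled; avoidable losses after allocation arise mainly if 6.1 is followed literally.

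No size should be attached. A reader might assign the whole 5% drop-out allowance (0.05 × 208 = 10.4 patients) to the gap between allocation and treatment. Section 11.2 does not say when drop-outs occur, and 11.5 expects no missing primary outcomes. A reader might also express a baseline shift as a share of the target difference of 3. No shift is documented, and the adjusted model reports odds ratios rather than mean differences. Nor do the documents show that the randomised comparison is broken.

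The conclusion assumes that swab yield can vary with the operator's technique and that the operator can see the allocation. The plan excludes neither.

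**What to change.** State one order, in the same words, in 6.1, 9.3.2 and Table 1 (and in the flow chart if it differs):

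1. consent reconfirmed;
2. patient intubated and eligibility confirmed;
3. baseline swab taken;
4. allocation opened in REDCap during the existing 3-minute wait.

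The cost is protocol wording and a note in the theatre work instruction. It adds no visit, sample or minute.

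Two limits should be recorded. Reordering shortens the window for loss after allocation but does not change the FAS definition or the replacement rule; limiting replacement to subjects not yet randomised would close that remaining gap. It also does not blind the 5-minute swab that carries the primary outcome, which is a separate issue needing its own remedy.
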